1.5 Trial Design

An open label study in 250 subjects over five years. We are planning 130 subjects with COPD (varies stages of GOLD I-IV) and 120 normal subjects (non-smokers, ex smokers and current smokers with normal PFT's).

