We have initiated a proof of concept study under IND 104,917 and with local IRB approval (Evaluation of Regional Ventilation in Normal Subjects and Subjects with Airway and Lung Disorders Using 19F Magnetic Resonance Imaging of Inert Perfluorinated Gases mixed with Oxygen (PFP): A Phase 1 Study). We have consented 44 subjects minus one withdrawal, screened 43 subjects in the study with the characteristics described in Table 1 and scanned 30 subjects (reasons for non scanning of subjects: 1 voluntary withdrawal prior to any study participation, 5 body habitus (too obese), 4 screen fails, 4 MRI contraindications).

Disease Status	Number of Subjects Screened (F/M)
Normal	13 (5/8)
COPD	11(7/4)
COPD, Emphysema	4 (1/3)
COPD Emphysema, Asthma, Small Airway Disease	1(1/0)
COPD Asthma, Small Airway Disease	1 (1/0)
Asthma	2 (2/0)
Asthma, small airway Disease	2 (2/0)
Cystic Fibrosis	5 (4/1)* all with lung transplant
Lung Transplant	2 (1/1)
Small Airway Disease	1 (1/0)
Unknown Etiology	1 (0/1)
Total	43 (25/18)

Table 1: Disease profiles of screened subjects in the phase 1 proof of concept study

2 Trial Objectives

The proposed study will determine regional qualitative and quantitative lung function information in the context of the clinical trajectory of COPD defined by the cross sectional cohort components. Due to the long time-frame of this disease we are using a modified case control design that allows a cross-sectional evaluation of the proposed measures in aims 1-2 to identify putative markers that could later be tested as prognostic factors in longitudinal studies. In the case of these PFx/oxygen mixtures, the availability of multi-liter quantities allows for wash-in/wash-out image acquisition and analysis allowing direct measures of gas trapping in a manner not easily achieved with any existing modality.

3 Trial Design

The central hypothesis and current observation is that PFx gases used as contrast agents provide functional images of the lung airways including important regional ventilation information such as ventilation defect severity and gas trapping. We will test the central hypothesis and accomplish the overall objective by addressing the following specific aims:

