3.1 Primary Study Aims/Secondary Aims

Aim 1: Determine quantitative measures of lung ventilation performance in terms of direct measures of gas trapping measured during washout of the perfluorinated gas mixture.

Sub-aim 1.1: Compare gas trapping from aim 1 with air trapping by HRCT using conventional analysis procedures.

Sub-aim 1.2: We will accomplish this aim (as well as Aim 2) in a well-characterized cohort of subjects with COPD and subjects with normal global pulmonary function tests (non-, ex- and current smokers). This cohort will provide the basis for the cross sectional evaluation of the imaging markers in all aims with respect to disease severity (e.g. GOLD status) and risk factors (e.g. smoking)

Aim 2: Determine ventilation defect severity by comparing regional gas signal during wash-in of the perfluorinated gas mixture to steady state in the same cohort.

The outcomes of the work proposed in the aims is expected to demonstrate a novel quantitative approach for ventilation defect and gas trapping evaluation of regional lung function in humans that would be easily deployed for multi-center studies. It should also provide a set of biomarkers that could better inform evaluation of new treatments.

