6.1 Statistical Methods and Subject Population for Analysis

We have three main methods to employ to characterize of clinical phenotypes using MR Imaging bases features.

One method is to estimate with reasonable precision the mean and standard deviation ventilation parameters from 19F gas imaging. So with 250 (5 groups) subjects we should be able using a t-test (or ANOVA) to detect a variation in defect volume of approximately 6% in the smallest sample (N = 26/group, GOLD III/IV) (alpha 0.05 and 90% power) and 5% in the reference groups (N=40/group). [Statmate Ver 2, GraphPad Software (La Jolla, Ca)].

Further, we wish to evaluate the diagnostic/prognostic ability of the MRI parameters to provide distinction among current ‘phenotypes’ and perhaps extend better discrimination with the MRI parameters from study aims. We will also use statistical modeling for this project to correlate the features obtained from the gas-probe MR imaging-based measures with one or more of the clinical assessment measures recorded in Aim 1.2, to better characterize disease phenotypes and identify the most promising prognostic indicators.

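### Does the 90% power claim in section 6.1 hold for only one unadjusted two-group t-test, so that a five-group comparison is underpowered or error-prone?

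*Combined protocol and SAP*

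**What the plan says.** Section 6.1 lists estimation as the first of three methods: the aim is to "estimate with reasonable precision the mean and standard deviation ventilation parameters" from the gas images. The power statement follows directly: "So with 250 (5 groups) subjects we should be able using a t-test (or ANOVA) to detect a variation in defect volume". The plan puts the detectable difference at roughly 6% in one setting and 5% in another, and describes the two settings in these words: "in the smallest sample (N = 26/group, GOLD III/IV) (alpha 0.05 and 90% power) and 5% in the reference groups (N=40/group"). The section does not give the SD behind these figures, whether the test is one- or two-sided, which pairs of groups are meant, or a multiplicity rule.

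Section 1.5 describes the cohort as "130 subjects with COPD (varies stages of GOLD I-IV) and 120 normal subjects (non-smokers, ex smokers and current smokers with normal" lung function). Sub-aim 1.2 in section 3.1 will evaluate the "imaging markers in all aims with respect to disease severity (e.g. GOLD status) and risk factors (e.g. smoking"). Section 2 (Trial Objectives) gives the purpose of the cross-sectional design: "to identify putative markers that could later be tested as prognostic factors in longitudinal studies".

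**The concern.** A t-test compares two groups, and an ANOVA over five groups tests a different hypothesis with a different power function. One pair of detectable differences attached to either test looks as if it was computed for the simpler one and carried over to the other. Three consequences would follow.

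- **False positives.** Five groups form ten pairs. If each pair were t-tested at 0.05, the chance of at least one false difference would be well above 5%.
- **Power.** If pairs were controlled jointly and the figures came from an unadjusted test, the real power would be below 90%. A null result between smoking groups would then be read as stronger evidence than it is.
- **Group structure.** The sizes 26 and 40 per group, five groups and 250 subjects do not give a design that contains both a 26 v 26 and a 40 v 40 comparison.

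**Working it through.** **Inputs.** From section 6.1: alpha 0.05, power 90%, 6% at 26 per group, 5% at 40 per group, five groups, 250 subjects. From section 1.5: 130 COPD and 120 normal subjects. Assumed, because not stated: two-sided testing and one SD common to all groups. The SD is solved for.

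**1. Reproduce the stated figures with an unadjusted t-test.** Power is P(T > c), where T is noncentral t with noncentrality difference / (SD × √(2/n)) and c is the critical value. For n = 26, df = 50 and c = 2.009; 90% power needs a standardised difference of 0.917, so SD = 6 / 0.917 = 6.54. For n = 40, df = 78 and c = 1.991; the standardised difference is 0.734, so SD = 5 / 0.734 = 6.81. A common SD of 6.7 gives detectable differences of 6.7 × 0.917 = 6.14 and 6.7 × 0.734 = 4.92, which round to the stated 6 and 5. The two figures agree with each other.

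**2. Try the design they are said not to fit.** For Tukey over five groups (df = 245), c = q/√2 = 2.748. Solving the same equation for 90% power gives SD 5.36 (6% at 26) and 5.54 (5% at 40).

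| Procedure | SD from 6% at 26 | SD from 5% at 40 | Common SD | Power, 26 | Power, 40 |
|---|---|---|---|---|---|
| Unadjusted t-test | 6.54 | 6.81 | 6.6 | 0.895 | 0.917 |
| Five-group Tukey | 5.36 | 5.54 | 5.4 | 0.895 | 0.917 |

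The two fits cannot be told apart. Other designs can be back-solved too: Bonferroni over ten pairs (alpha 0.005) needs SD 5.08 and 5.33, and an ANOVA with two groups at the extremes and three midway needs 5.41 and 5.63. The stated ratio 6/5 = 1.20, against √(40/26) = 1.24, reflects the sample sizes and not the test.

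**3. False-positive rate.** Ten unadjusted pairs among five groups with equal means: the studentized range distribution at √2 × t(0.975; 245), with df = 245, gives 0.284. Simulation over several equal and unequal splits gives 0.278 to 0.286. The figure of 28% is right for that analysis. The omnibus ANOVA gives 0.05.

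**4. Power under joint control depends on the SD.** Assume group sizes 40/40/40/104/26.

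| Comparison | Tukey, SD 6.81 to 6.54 | Tukey, SD 5.4 | Unadjusted, SD 6.81 to 6.54 |
|---|---|---|---|
| 5% at 40 v 40 | 70–75% | 92% | 90–92% |
| 6% at 26 v 40 | 77–81% | 95% | 93–95% |
| 6% at 26 v 104 | 90–92% | 99% | 98–99% |

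For the omnibus ANOVA at SD 6.81 to 6.54, power is 74–78% when two reference groups are 5 apart and the rest midway. In the other three patterns examined it is about 94% or more: one reference group raised by 5; GOLD III/IV raised by 6; and a 0/0/0/3/6 gradient. At SD 5.4 even the least favourable pattern has about 93%.

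**5. Group sizes.** Three reference groups of 40 make 120, which matches the normal cohort. Two COPD groups then share 130; if one has 26, the other has 130 − 26 = 104. That split has no 26 v 26 pair. The alternative 120 + 78 + 26 + 26 = 250 (78 in GOLD I and II, 26 each in III and IV) has a 26 v 26 pair but no group of 40. So the split of the COPD subjects cannot be recovered. Under the first split, however, the contrasts that involve the group of 26 exceed 90% unadjusted at SD 6.5 to 6.8 (step 4).

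**The case for a change.** The strongest case for a change does not need the SD. A power statement should let a reader identify the comparison it describes, and this one does not: the SD and its source, the sidedness, the five groups and the contrasts are all missing. With all 250 subjects allocated and normal and COPD subjects kept apart, no five-group split holds both a 26 v 26 and a 40 v 40 pair. Sub-aim 1.2 makes disease severity and smoking axes of evaluation, so several comparisons are to be expected. The plain reading of alpha 0.05 is an unadjusted test. If that is right and all pairs were later controlled, the 40 v 40 smoking comparison would fall to 70–75% power. A few words in section 6.1 would settle all this at no cost in subjects.

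The omissions are real, and that part stands. The rest is conditional. Tukey and ANOVA also run at an overall alpha of 0.05, so the wording does not single out an unadjusted test. The shortfall needs two things that the plan does not say: that the SD was about 6.5 to 6.8, and that all pairs will be controlled. The 28% needs a third: that all ten pairs will be t-tested without control. A detectable difference quoted per group is also a common planning shorthand and need not describe a literal contrast of two groups of 26.

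**Conclusion.** No change to the plan is called for. No stated figure is shown to be wrong: 6% and 5% agree with each other to rounding under an unadjusted t-test (SD about 6.5 to 6.8) and equally under five-group Tukey (SD about 5.4 to 5.5). Both sets of SDs are inferred and assume two-sided testing with equal variances. The shortfall under joint control ranges from none, at SD 5.4, to about 20 percentage points for the 40 v 40 comparison, at SD 6.81. The documents do not say which applies.

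The missing details limit how far a reader can check the calculation, but they do not block the analysis. When the data are in, the groups follow from smoking and GOLD status, the SD is observed, and ANOVA with or without a pairwise procedure is a routine choice. Whether to control all pairs is a fair trade-off here: the study looks for candidate markers to be tested later, the power statement sits under an estimation aim, and the main modelling in section 6.1 selects predictors by AIC. No confirmatory decision rests on one pairwise p-value. If unadjusted pairwise results are reported, they should be read as exploratory, which fits the purpose stated in section 2.

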In a similar context, a recent study has shown such promise for certain CT imaging-based features (7). Thus, if the role of MR imaging-based measures can be established in a similar fashion then, associated with a link f , is some MR-defined variable Z which can define a biomarker, risk factor or phenotype R , resulting in the general linkage statement of $R \leftarrow f \rightarrow \text{GOLD+MRI}$. The makeup of this biomarker would contain information obtained from one or more measures Aims 1, 1.1 and 2 as well as other clinical status information X (as codified in the GOLD score or more generally some combination of the demographic, physiological and past history information, (Aim 1.2). This biomarker would then provide a more rapid and efficient means for deciding treatment strategies. We will examine the diagnostic/phenotyping ability of the MR imaging-based features (Aims 1 and 2) in terms of their ability to predict existing clinical phenotypes (GOLD) characterized and other clinical features (Aim 1.2). For this purpose, we will divide the predictors into two categories: a) clinical assessments features ($X_{a1}, X_{a2}, \dots, X_{ak}$), obtained from existing clinical, physiologic, and HRCT imaging, measured under Specific Aims 1.1 and 1.2; b) features obtained from MR imaging ($X_{b1}, X_{b2}, \dots, X_{bl}$), identified under Aims 1 and 2. A generalized linear model of the form [1] will be fitted using the method of maximum likelihood:

$$g(Y_t) = \beta_{a0} + \beta_{a1}X_{a1} + \dots + \beta_{ak}X_{ak} + \epsilon \quad [1]$$

The predictability of this model will be calculated using the Akaike Information Criterion (AIC) statistic (2), which balances the quality of fit (likelihood) against model complexity (8). Selection of the optimal subset of predictors will be achieved via a search over predictor space to identify the subset that maximizes the AIC statistic.

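### The only model equation in section 6.1 has no MR term and no defined outcome, and its AIC rule runs the wrong way under the usual definition

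*Combined protocol and SAP*

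**What the plan says.** Section 6.1 says that the MR features will be assessed "in terms of their ability to predict existing clinical phenotypes (GOLD) characterized", together with other clinical features from Aim 1.2. For this, "we will divide the predictors into two categories". The clinical set X_a is "obtained from existing clinical, physiologic, and HRCT imaging, measured under Specific Aims 1.1 and 1.2". The MR set X_b comes from Aims 1 and 2.

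The model is then introduced: "A generalized linear model of the form [1] will be fitted using the method of maximum likelihood". The equation printed is "g(Y_t) = \beta_{a0} + \beta_{a1}X_{a1} + \dots + \beta_{ak}X_{ak} + \epsilon". No second equation follows.

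The section describes AIC as a balance of fit against complexity, gives no formula, and says that a search over the predictors will "identify the subset that maximizes the AIC statistic".

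Among the stated aims of the section is to "perhaps extend better discrimination with the MRI parameters from study aims".

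**The concern.** The section asks what MR adds, yet no X_b term appears in the one model written out. The plan does not say whether X_b is to be fitted alone, added to X_a, or pooled with X_a in one search. These answer different questions, and only a comparison of X_a with X_a + X_b shows whether MR improves discrimination beyond clinical data. With Y_t undefined, neither the link function nor the set of admissible predictors can be fixed.

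The selection rule is a separate problem. If X_b is supplied and the rule is then followed as printed with the usual AIC, the search prefers the worst penalized fit. The two faults are alternatives, not cumulative: with [1] taken literally there is no MR feature for the search to discard.

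What is at stake is the marker-finding aim in section 2, which looks for candidates to test later in longitudinal studies.

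**Working it through.** The plan gives no figure for this model, so there is none to reproduce. The check is of the text, followed by illustrations.

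1. **Terms in [1].** There is an intercept and k clinical terms. The number of X_b terms is 0, so [1] as printed estimates no MR effect. It also puts an additive error on g(Y_t); a generalized linear model is written for g(E[Y]) and has no such term.

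2. **Direction of AIC.** With AIC = 2k − 2logL, a better fit raises logL and lowers AIC. Adding one predictor changes AIC by 2 − LR, where LR is the likelihood-ratio chi-square on 1 df. Minimizing keeps the predictor when LR > 2; maximizing keeps it when LR < 2, that is, when it is uninformative. Maximizing would be right for an opposite-sign criterion such as logL − k, but section 6.1 gives no such definition.

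3. **Illustration of step 2.** From section 1.5: 130 COPD and 120 normal subjects. Assumed: Y = COPD status; three clinical candidates (one with AUC 0.70, two noise); three MR candidates (one informative, two noise); normally distributed features; all 64 subsets searched; 300 runs per setting. The documents give no MR AUC, so three values were tried.

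| Assumed MR AUC | Informative MR feature kept, minimizing | Kept, maximizing |
|---|---|---|
| 0.65 | 298/300 | 0/300 |
| 0.75 | 300/300 | 0/300 |
| 0.86 | 300/300 | 0/300 |

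This follows almost directly from step 2. It shows direction and is not a forecast for this trial.

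4. **Testing after a search.** If MR features are picked by AIC and the chosen set is then tested against the clinical model by an ordinary likelihood-ratio test, the error rate is not 5%. With three independent noise features, the chance that at least one is nominally significant is 1 − 0.95³ = 14.3%. Simulating the full search and test with three noise MR features gave about 16% false positives.

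5. **Outcome-defining predictors (conditional).** Section 3.3.1 includes spirometry among the screening tests. Section 4.1 confirms COPD by FEV1/FVC < 0.70, and section 4.2 determines normal status by spirometry. X_a covers physiologic features without listing them.
   - If Y were COPD status, X_a held FEV1/FVC and the ratio separated the groups completely, logL would tend to 0. AIC would then tend to 2 × 2 = 4, and to 2 × 3 = 6 with an MR term, so MR could not enter.
   - With some overlap, under assumed uniform ratios and MR independent of the ratio within group, the results at MR AUC 0.65, 0.75 and 0.86 are as follows. After clinical features that do not define Y, the median LR for MR is 16, 46 and 103. After FEV1/FVC, with 2.5–10% of normals at a ratio of 0.65–0.70, it is 1.3–2.5, 3.5–7.4 and 8.4–16.3. Minimized AIC then keeps MR in 39–57%, 67–90% and 86–99% of runs.
   - At 1% overlap it is kept in 25%, 43% and 58% of runs. But 0.99¹²⁰ = 0.30, so about 30% of those runs have no overlap and separate completely. With at least one overlapping normal forced into each run, the shares are 31%, 52% and 77%.
   - GOLD stage was not simulated, because the documents do not give its cutoffs.

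**The case against.** The strongest reply is that these are drafting slips with recoverable intent. The section names MR as the object of study, defines X_b for the purpose, speaks of a model of the form [1], and seeks an optimal subset by balancing fit against complexity. A competent analyst would add X_b and minimize AIC. The modelling is also exploratory. All of this is fair. It limits the weight of the point, but it does not say how X_b enters, and a prespecified rule should not depend on the analyst overriding it.

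Three stronger readings are tempting, and the documents do not support them:

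- **That the plan contains no analysis of MR features.** Section 6.1 also plans t-test/ANOVA comparisons of ventilation parameters and modelling that correlates MR features with clinical measures. Neither is affected.
- **That the model is circular.** Nothing places FEV1/FVC in X_a, and binary COPD status is never named as Y. Physiologic features could mean lung volumes or DLCO. What is missing is a safeguard.
- **That GOLD is both outcome and predictor in [1].** The GOLD score is named as clinical information where a conceptual biomarker is described as containing "information obtained from one or more measures Aims 1, 1.1 and 2 as well as other clinical status information X". That passage does not define the X_a of [1], so the overlap is an ambiguity.

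**Conclusion.** The point holds as an error of specification. Equation [1] omits the MR terms that the section exists to assess, Y_t is undefined, and the AIC rule is in the wrong direction unless an unstated opposite-sign definition is meant. These conclusions rest on the text alone and are firm. It should be fixed before analysis.

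The concern over outcome-defining predictors is secondary and conditional on choices the plan has not made. Its figures depend on assumed distributions, assumed MR AUCs and an assumed outcome. They show that the added value of MR could be understated, more in the size of the LR than in whether a strong MR feature is selected. The low ends at 1% overlap partly reflect complete separation and should not be quoted as effects.

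**What to change.** In section 6.1:

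- Define Y for each analysis, with its distribution and link.
- Write a base model, g(E[Y]) = linear predictor in X_a, and an extended model, g(E[Y]) = linear predictor in X_a and X_b, with no additive error term.
- State AIC = 2k − 2logL and select the subset with the smallest value.
- Judge the added value of MR by comparing the two models with a prespecified X_b set. If X_b is chosen by the search, use a method that repeats the whole search, such as cross-validation or the bootstrap, and not an ordinary likelihood-ratio test.
- List the X_a variables. For each Y, leave out those that define it: FEV1/FVC if Y is COPD status; the GOLD score and the measurements used to assign it, which the SAP should name, if Y is GOLD. They can stay for outcomes they do not define, such as six-minute walk or the St George score.

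The cost is SAP wording. All the variables are already collected at screening and at the MRI visit.

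### Predictability is judged by the same AIC that drives the predictor search, with no internal validation named, so useless features can be retained and credited with value

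*Combined protocol and SAP*

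**What the plan says.** Section 6.1 divides the candidate predictors into two sets. The first is clinical, "obtained from existing clinical, physiologic, and HRCT imaging, measured under Specific Aims 1.1 and 1.2". The second is "features obtained from MR imaging" under Aims 1 and 2. The sizes of the sets are left as symbols. The targets are GOLD phenotype and other clinical features.

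On fitting: "A generalized linear model of the form [1] will be fitted using the method of maximum likelihood". On assessment: "The predictability of this model will be calculated using the Akaike Information Criterion (AIC) statistic", with the remark that AIC trades fit against complexity. On selection, the subset is found "via a search over predictor space to identify the subset that maximizes the AIC statistic".

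The sample is given in section 1.5: "An open label study in 250 subjects over five years", made up of 130 with COPD and 120 normal. Section 2 says that markers found here might be tested later in longitudinal studies. Section 6.1 says the resulting biomarker would offer a quicker way to decide on treatment.

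**The concern.** One statistic does two jobs: it picks the model, and it is the stated measure of how well that model predicts. This raises two problems.

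- **AIC is a relative criterion.** It ranks models fitted to the same data. It gives no error rate, discrimination or calibration from which a reader could tell whether a model predicts well.
- **The winning AIC is optimistic.** The penalty is set for one specified model. When many subsets are compared, the best value is partly chance, and nothing in the plan corrects for that.

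At stake is the credit given to the MRI features. Section 6.1 hopes that they improve discrimination between phenotypes, yet the plan has no step that would separate real improvement from the product of a search. Markers carried forward to longitudinal studies, or proposed to guide treatment, could include some with no value.

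**Working it through.** The plan states no figure for predictability, so there is none to reproduce. The detectable differences in section 6.1 (about 6% with 26 per group, 5% with 40 per group) concern group means and do not bear on this point.

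**Inputs from the documents.** 250 subjects, 130 COPD and 120 normal (section 1.5); maximum likelihood fitting and a search on AIC (section 6.1).

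**Assumptions.** A binary outcome (COPD v normal) with logistic regression; 5, 10, 20 or 30 candidates, because the number is not given; independent standard normal predictors; a stepwise or forward search for the lowest AIC; AUC as the yardstick, although the plan does not name it.

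**Step 1: one useless predictor.** Adding one parameter lowers AIC (−2 log-likelihood + 2 × parameters) when the likelihood-ratio statistic exceeds 2. For a useless predictor that statistic is approximately chi-square with 1 df, so P(chi-square > 2) = 0.157.

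**Step 2: several useless predictors.** The chance that at least one of m independent candidates lowers AIC is 1 − (1 − 0.157)^m. This is 57.5% for m = 5, 81.9% for 10, 96.7% for 20 and 99.4% for 30.

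**Step 3: simulation with noise only, 250 subjects.**

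| Candidates | Mean kept | Apparent AUC | AUC in new subjects | 10-fold CV, search repeated in each fold |
|---|---|---|---|---|
| 5 | 0.9 | 0.55 | 0.50 | 0.50 |
| 10 | 1.5 | 0.57 | 0.50 | 0.48 |
| 20 | 3.1 | 0.61 | 0.50 | 0.50 |
| 30 | 5.4 | 0.65 | 0.50 | 0.52 |

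The first columns rest on 120 to 300 data sets per row. The cross-validated column rests on 60, and on 25 in the last row. Separate forward-selection runs gave 0.8 to 4.9 kept and apparent AUC 0.54 to 0.65. Across the range, the AIC of the selected model beat the empty model by 1.4 to 9.4 units on average, so the plan's own statistic also favours noise.

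**Step 4: real signal present.** One real predictor and 19 noise candidates, forward search, 100 data sets each:

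| Standardised difference of the real predictor (assumed) | Apparent AUC | True AUC | Inflation |
|---|---|---|---|
| 0.8 | 0.748 | 0.688 | 0.060 |
| 1.5 | 0.869 | 0.841 | 0.028 |
| 2.0 | 0.932 | 0.910 | 0.022 |

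A repeat with 400 data sets gave inflation of 0.055, 0.031 and 0.022. About three noise features were kept in every setting.

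**Step 5: apparent added value of useless MRI features.** One clinical predictor (assumed difference 1 SD) is always kept, and the search runs over useless features only.

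- With 10 useless features, at least one is kept in about 84% of data sets. AUC appears to rise by 0.014 and truly falls by 0.013.
- With 20, the figures are 96%, a rise of 0.025 and a fall of 0.024.

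**The case against.** Several objections have force.

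- **AIC is not naive.** It penalises complexity, and for a single prespecified model this partly corrects for optimism. That stands. What remains uncorrected is the search.
- **All-noise is the worst case.** COPD is confirmed by spirometry under section 4.1, and the candidates include physiologic and HRCT measures, so strong real signal is likely. A reader might take the gap of 0.61 v 0.50 at 20 candidates as the expected bias in this trial. The documents do not support that; Step 4 shows a much smaller inflation once a real predictor is present.
- **It is tempting to say that useless predictors will look predictive.** That is too strong. With five candidates the chance of keeping any is little better than even, and the number of candidates is not stated.
- **The plan does not promise an AUC.** It would be wrong to say that it will report an inflated one. AUC is used here only to put the effect on a readable scale.
- **Same-data evaluation and a binary outcome are inferences.** The first follows from the absence of any split or resampling. The second is a simplification, since section 6.1 speaks of GOLD, other features and five groups.
- **The modelling is one of three methods in section 6.1 and is exploratory.** Section 2 speaks of putative markers for later testing. A reader might infer that the whole trial is compromised. It is not: measuring gas trapping and ventilation defects under Aims 1 and 2 does not depend on this model.

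These objections reduce the size and weight of the point. They do not supply the missing validation. Possible later studies are not internal validation, and section 6.1 itself links the biomarker to treatment decisions.

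**Conclusion.** The point holds as a recommended change to an exploratory component. The plan judges predictability by the criterion it searches on and names no internal validation, so useless features can be retained and credited with value.

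Under the stated assumptions, noise alone yields about 1 to 5 retained features and apparent AUC of about 0.54 to 0.65 against 0.50. With one real predictor and 19 noise features, AUC inflation is about 0.02 to 0.05, reaching 0.06 in one run at the weakest signal. The more durable harm is that about three noise features are still selected, and that useless MRI features can show a small apparent gain while prediction worsens.

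The exact size in this trial cannot be known. It depends on the number of candidates, their correlation, the form of the outcome and the real signal. The point is separate from the direction in which AIC is optimised; correcting that direction would leave this problem in place.

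**What to change.** Revise section 6.1 as follows.

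1. List the candidate predictors in each set and the outcome or outcomes to be modelled.
2. Use AIC only to rank candidate models.
3. Report performance corrected for optimism by bootstrap or repeated 10-fold cross-validation, repeating the whole search in each resample. Choose a measure that suits the outcome: for example, AUC or c-index with calibration for binary or ordinal GOLD, and prediction error for continuous features.
4. Report the added value of MRI as the corrected difference between the clinical-only and the clinical-plus-MRI model.

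Other sound forms of internal validation would also serve. In the noise-only simulation, cross-validation with the search inside brought the AUC back to about chance (0.48 to 0.52). The change uses data already planned and needs no further subjects or procedures. It costs a paragraph, computing time and a somewhat lower reported performance.
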